These evidence of long-term organ damage, symptom burden, and functional impairment lead healthcare providers to wonder if it is possible to predict who will develop Long COVID. While results from some studies showed that the severity of acute COVID-19 symptoms associate with Long COVID [6, 15], a study pointed out that there is no relationship between disease severity and chronic fatigue post COVID recovery [9]. Instead, female and history of psychological distress may associate with prolonged fatigue [9]. Another study recruited more than four thousand patients in UK found that older age, increasing BMI, female sex, and experiencing more than five symptoms during the first week of illness were associated with Long COVID [16]. In a similar vein, female sex and overweight/obesity were found to be related to lower HRQOL in survivors [13]. In short, the severity of acute symptoms, preexisting comorbidity, female gender, and BMI or weight are all potential predictors of Long COVID [6, 9, 13, 15, 16]. With that being said, current evidence is premature to determine what can predict the existence or severity of Long COVID at different stage of survivorship.

-Guideline for Current Practice

In order to managing Long COVID, National Institute for Health and Care Excellence (NICE), the Scottish Intercollegiate Guidelines Network (SIGN), and the Royal College of General Practitioners (RCGP) published a rapid guideline in December, 2020 [17]. In this NICE guideline, symptoms of COVID-19 are categorized as acute (i.e., signs and symptoms for up to 4 weeks), ongoing (i.e., signs

and symptoms from 4 to 12 weeks), and post-COVID-19 syndrome (i.e., signs and symptoms continue for more than 12 weeks and are not explained by an alternative diagnosis). It recommends that healthcare providers should be aware of possible symptoms, actively discuss with survivors in terms of their symptom experience and how symptoms affect their function and life, offer chest X-ray by 12 weeks after acute COVID-19, offer an exercise tolerance test, and consider referring survivors to an integrated multidisciplinary assessment. It also stressed the importance of long-term follow-up with symptom changes. However, upon the time of guideline development, accessible evidence was still scarce and of poor quality [7]. Furthermore, while the guideline repeatedly mentioned the needs to discuss symptom impacts on function and life, relevant reference is even less available.

The Knowledge Gap

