Sampling and Recruitments. Inclusion criteria are individuals who are (1) at least 20 years-old and (2) diagnosed with COVID-19 within six months. Exclusion criteria are individuals who (1) are still in the active phase of COVID-19 infection (i.e., diagnosed within 4 weeks) and (2) have cognitive impairment or other issues that prevents them from doing self-ratings of symptoms via phone interviews. The estimated sample size is about 98 subjects based on G*Power 3.1.9.4 calculation (effect size $f^2=0.15$, $\alpha=0.05$, $\beta=0.2$, 6 predictors). Considering the loss of follow-up rate of 20%, 118 subjects are needed.

Potential subjects will be identified through the following strategies: (1) searching the intranet of participating medical institutions (e.g., National Taiwan University Hospital, National Yang Ming Chiao Tung University Hospital and Min-Sheng General Hospital), (2) recruitment messages posting on social media, and (3) referrals from collaborating healthcare providers. After participants fill out the online questionnaire, research assistant will approach potential subjects via phone to explain the research, explore their willingness, and screen for eligibility. Individuals who are eligible and agree to participate in the study will receive documents of study information and consent form by mail. Participants are required to mail back the signed inform consents.

Upon the receiving the signed inform consents, the subjects will be followed immediately to confirm participation and collect demographic data. They will then be regular followed up at 3 (for those who are participated within 3 months of COVID diagnosis), 6, 9, and 12 months (T1-4) from the diagnosis of COVID-19. During these regular follow-ups, subjects will need to report health status indicators and rate their symptom severity and HRQOL based on selected instruments. Subjects will have access to a line group managed by the research team. They can communicate with the research team regarding any issues of research or symptoms through line group. All data collection will be occurred via online questionnaire, phone or video call interview (e.g., +Google meet or line video call). Paper documents, such as inform consents, will be stored in the locked cabin located at National Taiwan University School of Nursing. Electrical data will be managed and stored using Redcap and encrypted Dropbox.

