Statistical methods. In addition to use descriptive statistics to describe the characteristics of participants and symptoms, one-way repeated measures analysis of variance (ANOVA) will be employed to determine whether there are any differences of symptom severity along the four time points (aim 2). Binomial logistic regression will be selected to predict a dichotomous dependent variable (i.e., existence of Long COVID) given multiple independent variables. Multiple linear regression will be used to predict continuous dependent variable (i.e., symptom severity) given multiple independent variables (aim 3).

Table 1. Long COVID Symptoms Mentioned by Example Studies and Instruments

First Author of the Studies or Instrument	Lopez-Leon	Romero-Duarte	EORTC-QLQ30	LC29
Fatigue	58%	22-34%	V	-
Pain	11%	-	V	V
Joint pain/ muscular pain	19%	15.3%	-	V
Muscle weakness	-	3.8%	-	V*
Weight loss	17%	-	-	V
Alopecia	25%	3%	-	V
Red eyes	6%	-	-	V
Cutaneous signs	12%	1.5-3.1%	-	V
Dyspnea	24%	28%	V	V
Polypnea	21%	-	-	V
Cough	19%	19.2%	-	V
Throat pain	3%	8.4%	-	V
Chest discomfort	16%	6.6%	-	V
Rib pain	-	4.5%	-	V
Headache	44%	5.3%	-	V*
Anosmia/ loss of the sense of smell	21%	-	-	-
Ageusia/ loss of the sense of taste/ dysgeusia	23%	7.2%	-	-
Paresthesia	-	3.4%	-	V
Attention disorder	27%	-	V	-
Memory loss	16%	-	V	-
Dizziness	3%	1.9%	-	V
Depression	12%	4.4%	V	-
Anxiety	13%	6.8%	V	-
Mood disorder	2%	-	V	-
Dysphoria	2%	-	-	-
Sleep disorder	11%	4.9%	V	-
Palpitation	11%	3.1%	-	-
Diarrhea	-	10.3%	V	
Constipation	-	1.8%	V	-
Abdomen pain	16%	5.4%	-	V*
N/v	58%	2%	V	-
Anorexia	11%	1%	V	-

Note. Table 1 compares the Long COVID symptoms mentioned by example studies and selected instruments. The percentage represents how many people have reported specific symptoms in the study. The check mark represents symptoms addressed in the instrument. Grey shading highlights symptoms that are not covered by EORTC QLQ30 or LC29. The instrument uses different terminology to describe the symptom.

Qualitative strand

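### Aim 3 uses ordinary single-outcome regressions for outcomes measured at up to four visits and does not say how the repeated measurements enter; a repeated-measures model on all visits would serve it better

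*Combined protocol and SAP*

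**What the plan says.** The Statistical methods paragraph of the quantitative strand gives aim 3 two models. For the binary outcome: "Binomial logistic regression will be selected to predict a dichotomous dependent variable (i.e., existence of Long COVID) given multiple independent variables". For the continuous outcome: "Multiple linear regression will be used to predict continuous dependent variable (i.e., symptom severity) given multiple independent variables (aim 3". For aim 2, the same paragraph states that "one-way repeated measures analysis of variance (ANOVA) will be employed" across the four time points.

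Sampling and Recruitments sets the schedule. At each regular follow-up, "subjects will need to report health status indicators and rate their symptom severity and HRQOL based on selected instruments". The visits are at "3 (for those who are participated within 3 months of COVID diagnosis") and then at "6, 9, and 12 months (T1-4) from the diagnosis of COVID-19". A person therefore contributes up to four outcome measurements, or at most three if enrolled later than 3 months after diagnosis.

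The predictors are person-level: age, sex, chronic disease, smoking and BMI are listed as examples, plus symptom severity at diagnosis. The sample size of 98 is for a regression with six predictors, raised to 118 for 20% loss to follow-up. The background section on predictors gives the evidence gap as "current evidence is premature to determine what can predict the existence or severity of Long COVID at different stage of survivorship".

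**The concern.** Ordinary linear and logistic regression expect one independent outcome per person. The plan collects several and does not say which one is used, whether they are combined, or whether their correlation is modelled. Aim 2 has a repeated-measures method; aim 3 does not, and changing the aim 2 analysis would not alter the aim 3 regressions.

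Aim 3 is the analysis for which the sample size was computed. If the choice is left until the data are in, several analyses with different power and different error rates all fit the same sentence. Most of them also use the repeated outcomes less well than a standard longitudinal model would.

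**Working it through.** **Inputs from the plan:** f² = 0.15, alpha 0.05, beta 0.2, six predictors, 98 subjects, 20% loss, 118 enrolled (Sampling and Recruitments); up to four visits, with month 3 only for early enrolees; entry from 4 weeks to 6 months after diagnosis.

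**Assumed, because the plan gives no value:** within-person correlation ρ = 0.3, 0.5 or 0.7, equal between all visits; enrolment uniform over the entry window.

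**1. The plan's own figure.** Overall F test with df 6 and n − 7, noncentrality 0.15 × n. Power is 0.798 at n = 97 and 0.804 at n = 98, so 98 reproduces exactly, with one row per person. With 118 enrolled and 20% lost, 118 × 0.8 = 94.4; power at 94 is 0.78.

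**2. One visit per person.** For a predictor fixed over time, the information in one visit relative to m visits is (1 + (m − 1)ρ)/m.

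| ρ | loss, one of 3 visits | loss, one of 4 visits |
|---|---|---|
| 0.3 | 1 − 1.6/3 = 47% | 1 − 1.9/4 = 52% |
| 0.5 | 1 − 2.0/3 = 33% | 1 − 2.5/4 = 38% |
| 0.7 | 1 − 2.4/3 = 20% | 1 − 3.1/4 = 22% |

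**3. A separate model at each visit.** Four weeks is about 0.92 months. The share enrolled early enough for month 3 is (3 − 0.92)/(6 − 0.92) = 2.08/5.08 = 0.41. That is 118 × 0.41 = 48 people, or about 39 after 20% loss. Omnibus power is 0.42 at 48 and 0.33 at 39. If the share is instead 25% to 75%, about 24 to 71 people remain after loss and power is 0.18 to 0.63. Four tests of one null predictor give at most about 1 − 0.95⁴ = 18.5% chance of a false positive. That figure takes the tests as independent; correlated visits would give less.

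**4. A per-person summary.** With four visits for everyone, a mean divides the residual variance by m/(1 + (m − 1)ρ). Power at n = 98 is then 0.99, 0.96 and 0.91 for ρ = 0.3, 0.5 and 0.7. By design, however, some people have four visits and others three. A mean then covers different times since diagnosis, and an ever-present outcome gives early enrolees one more chance to be positive.

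**5. Stacked rows without adjustment.** The design effect is DE = 1 + (m − 1)ρ, and the true error of a 5% test of one coefficient is 2 × (1 − Φ(1.96/√DE)).

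| ρ | 3 visits: DE, error | 4 visits: DE, error |
|---|---|---|
| 0.3 | 1.6, 12% | 1.9, 16% |
| 0.5 | 2.0, 17% | 2.5, 22% |
| 0.7 | 2.4, 21% | 3.1, 27% |

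A null simulation with 98 people and four visits (4,000 runs) gave 16%, 23% and 28%. If 41% have four visits and the rest three, DE is 1.74, 2.24 and 2.74, and the error is 14%, 19% and 24%.

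**6. All of months 6, 9 and 12 in one model.** The information relative to one visit is 3/(1 + 2ρ) = 1.9, 1.5 and 1.25. With f² scaled by that factor at 94 completers, omnibus power is 0.98, 0.94 and 0.88, against 0.78 for one visit. This takes predictor effects as constant over the three visits.

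These power figures are for severity; none was computed for the logistic outcome.

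**The case against.** A reader might infer that aim 3 must either pool correlated rows with false standard errors or discard most of the data. The documents do not support that. Nothing says rows will be stacked, and the 98 fits one row per person. Per-visit models use every row across the set, and they and a per-person summary give valid standard errors. A single visit leaves 67–75% of rows unused, but the information lost exceeds half only at low correlation with four visits. The 12–27% error rates therefore belong to an analysis that the plan does not describe.

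A reader might also blame the small month-3 sample on the choice of regression. It comes from the entry window and the visit schedule, its size depends on an assumed enrolment pattern, and a mixed model would create no month-3 observations.

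Finally, aim 3 is exploratory, and the interest in stages of survivorship is background text, not part of the aim. Answers that differ between visits could be legitimate, and a pre-specified visit or summary would also remove the ambiguity.

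All of this stands as a limit on the point. It does not answer it: the plan states none of these routes, unequal visit counts complicate the summary route, and a single visit gives up information that has already been collected.

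**Conclusion.** The point holds as a gap in specification with a clearly better method available. It is not a finding that the planned standard errors are wrong. Relative to one visit per person, a joint model of months 6, 9 and 12 gives 1.25–1.9 times the information on fixed predictors, for ρ from 0.7 down to 0.3. This rests on assumed equal correlation and on effects constant over visits.

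The month-3 model is likely to fall short of 98, at about 39–48 people under uniform enrolment. Neither the planned size nor the 80% power should be taken to apply there. Inflated type I error is a risk only if rows are stacked without adjustment. The change should be made before analysis begins.

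**What to change.** Replace the two aim 3 models in Statistical methods:

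- **Severity:** a linear mixed model on all available visits, with visit (time since diagnosis) as a factor, the six predictors, and a within-person covariance (random participant effect or unstructured).
- **Existence:** a logistic GEE or mixed logistic model on all available visits, with visit as a factor and standard errors clustered on participant.
- **Stage-specific prediction, if wanted:** predictor-by-visit terms, labelled exploratory.
- **Per-visit regressions:** keep as secondary, with a statement that the 98 and its 80% power may not hold at month 3.

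The cost is a paragraph of text, slightly more analysis work, and reliance on a working covariance. No new data or participants are needed. If the sponsor prefers ordinary regression, the minimum is to name one primary visit or one per-person summary in advance and accept the loss shown above.

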**Using mixed-methods approach to explore the long-term
effects of COVID-19: presentations, associating factors, and
survivor experience**

NCT ID:_____ not yet assigned _____

Last update:12/02/2021 Version5

Abstract

Background. When the COVID-19 pandemic sustains for more than a year, a growing number of COVID-19 survivors have returned to their community. However, researchers warned that up to 80% of the survivors may experience multiple and severe long-term symptoms, sometimes called Long COVID, even they were asymptomatic or only had mild symptoms at diagnosis. These Long COVID can persist for longer than three months and cause profound distress and life interferences. Findings from studies and patient reports on social media suggest that various symptoms may be experienced, including fatigue, neurological symptoms, respiratory symptoms, and cardiovascular symptoms. With that being said, more areas, such as how Long COVID evolved after diagnosis, how we identify risk groups, and what are these survivors' needs, remain unclear. **Aim.** The overarching goal of this research project is to investigate the presentations and associating factors regarding Long COVID, and to explore survivor experience. The specific aims are to (1) integrate the state of science of Long COVID, (2) describe the changes of various symptoms and HRQOL after 3, 6, 9, and 12 months of COVID-19 diagnosis, (3) explore predicting factors of the existence and severity of Long COVID, and (4) explore how patient experienced COVID-19 symptoms. **Design.** It is a mixed-methods research project with embedded design. Among the three research stages, a systematical review will be conducted first to address aim one. In stage two, a longitudinal cohort study will be carried out to recruit and follow up with individuals diagnosed with COVID-19 for a year. During the follow-up, the participants will need to report their symptoms via online questionnaire, phone or video interviews (aim 2 and 3). Those who did experience COVID-19 symptoms will be invited to join stage three study. Stage three is a qualitative descriptive study addressing aim 4. **Participants and recruitment.** For stage two, the inclusion criteria are individuals who (1) are at least 20 years-old and (2) were diagnosed with COVID-19 within six months. Individuals who have cognitive impairment or other issues that prevents them from doing self-ratings of symptoms will be excluded. Potential participants will be identified through recruitment messages posting on social media and referrals from collaborating healthcare providers. **Expecting outcomes.** It is expected that Long COVID will pose huge burden on survivors and their families. This project can provide a solid reference to foresee possible problems in this population and formulate strategies for early detection and management. It is one of the few, if there is any, longitudinal study following up with COVID-19 survivors and including patients' perspectives.

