Taken it together, evidence has strongly supported the profound impact of Long COVID. However, there is still a huge knowledge gap regarding the trajectory, impacts, predictors, and interventions of Long COVID. For example, with regard to the symptom trajectory, most studies measured Long COVID at one time point, ranged from 14 to 180 days without defining ongoing and post-COVID-19 syndrome clearly [3, 4]. Less study observed symptom trajectory overtime. No evidence of symptom profile after 6 months of diagnosis is available. The way to identify symptoms also varies. Researchers selected various instruments or pre-determined lists of symptoms without clear rationale. Some research used chart review to identify symptoms. It is possible that some symptoms were ignored if they were not on the lists or does not documented in the medical record.

While emerging studies addressed the impacts of Long COVID on HRQOL and function, relevant data is still insufficient, including the HRQOL and function changes over time. To our knowledge, there is no qualitative studies describing symptom experience from survivors' perspectives. The changes of HRQOL and function is an important information for decision making of selecting palliative care and assessing rehabilitation needs. Lastly, most studies were completed in certain areas, such as US, UK, and other regions of Europe.

When "a worrying new wave of COVID-19 is hitting South-East Asia" [18], including Taiwan, it is imperative to follow up with these patients' symptom trajectory and experience comprehensively in order to monitor symptom burdens, identify needs, and manage symptoms early.

Methods

This is a **three-phase, mixed-methods research project with embedded design** (Figure 1.). Mixed-methods design is selected because it allows us to

comprehend the phenomenon from multiple aspects—the lack of information regarding longitudinal aspects and survivors' aspects is identified in the previous paragraphs. The following bullet points describe the embedded design according to the six key characteristics which are used to categorize and understand different mixed-methods designs [19].

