Instruments: assessing Long COVID symptoms. While there is no symptom or HRQOL instruments designed for COVID-19 survivors or patients with infectious disease, some HRQOL instruments designed for cancer patients may be an alternative choice. Specifically, as it is mentioned earlier in this proposal, in addition to respiratory symptoms, Long COVID seems to be systematical— just like symptoms caused by cancer and its treatment. Thus we propose to use European Organization for Research and Treatment of Cancer Quality of Life questionnaire (EORTC-QLQ

C30, Taiwan Chinese version) and lung cancer model (EORTC QLQ-LC29, Taiwan Chinese version) to measure Long COVID. In fact, among the 36 Long COVID self-perceived symptoms reported by Lopez-Leon's systematical review and Romero-Duarte's 6 months follow-up, these two questionnaires covered 29 of them (about 81%), including the most frequently reported ones (table 1). Three missing symptoms that are not covered by EORTC-QLQ-C30 or LC29 are anosmia, ageusia, and palpitation. These symptoms will be checked for existence separately during the follow-ups.

Both EORTC-QLQ C30 and LC29 are widely used by medical research and show good validity and reliability. EORTC-QLQ C30 consists of 30 items and measures patients' functions and symptoms by 4-point Likert scales. EORTC-QLQ C30 also measures quality-of-life (QoL) by 7-point Likert scales. While LC29 consists of 29 items, the subscales of 'fear of progression (2 items)' and 'surgery-related problems (5 items)' will not be used as they are related to cancer progression and treatment. The remaining 22 items will be rated by 4-point Likert scales in this study to measure additional symptoms. The Cronbach's alpha coefficient are above 0.70 and 0.73 for all items in EORTC-QLQ C30 and LC29 Taiwan Chinese version, respectively [21-23]. Higher scores for symptom scales represent more intense symptoms while higher scores for function scales and QoL means better function and QoL level. Example questionnaires are provided in appendix A and B.

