Recruitment. The approach of the qualitative strand is based on qualitative descriptive design because we want to provide a fundamental and straightforward description regarding the survivors' symptom experience. Participants who reported considerable symptoms at three-months follow-ups in phase two will be recruited purposively. Agreed participants will be offered informed consent forms to sign by mail and arranged a 40-50 minutes phone interview. According to the rule of thumb of qualitative study, approximately 30 participants are needed for the qualitative strand [24].

Data collection and analysis. All phone interviews are carried out by a trained research assistant who has relevant background (medical, nursing, or psychological). Field notes will be documented after each interviews. All recorded interviews will be transcribed verbatim.

Content analysis which is the common analytic strategy for qualitative descriptive studies will be used for data analysis in the qualitative strand. Content analysis is “a research technique for making replicable and valid inferences from text or other meaningful matter to the contexts of their use.[25]” Content analysis is flexible in terms of its approach and focus of analysis [26, 27]. The major process of content analysis generally includes the following processes: (1) deciding on the content to be analyzed, (2) selection of the unit of analysis, (3) condensation (i.e., reducing data while preserving the core), and (4) abstraction (i.e., creating codes and then grouping them into a hierarchy of categories based on their similarity) [26, 28]. Rather than following a linear direction, the process is interactive and is constantly modified based on the data [29]. The researcher will analyze the transcript data step by step:

Step 1: Transcript Review. The researcher will read through all transcripts several times to become immersed in the data and obtain a thorough understanding of the nature of the interactions that occur during the office visits. The researcher will construct memos about my impressions of each encounter and write a brief case description of each visit.

Step 2: Extraction of Text Units. In all of the transcripts, the researcher will highlight each text unit (e.g., phrase, sentence, story) related to symptom discussions. To aid in later organization of the data, the researcher will highlight data related to each major symptom (e.g., pain, fatigue, depression) with a different color or shading.

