There are some limitations of this projects. As a predetermined list of symptoms will be used to document Long COVID, it is possible that symptoms that

are not listed will be ignored. The qualitative strand is thus designed and hopefully to close the gap between experienced symptoms and reported symptoms. The recruitment will occur in certain hospitals and through online platform which may overlook some population, such as older age groups. The one-year longitudinal design also pose challenges to participant retention. Several strategies, such as convenient communication channel (e.g., line group) and participant compensation, will be employed to retain sufficient sample size.

Expecting outcomes

Results of this project will inform future practice, education, and research regarding managing Long COVID, which requires immediate attention and calls for evidence-based guideline. Specifically, based on the research aims, a systematical and comprehensive understanding of Long COVID will first outlined. This information can be used to advance practice guideline, stimulate intervention studies, and empower patients by helping them foreseeing possible symptoms. Secondly, by exploring the predicting factors, individuals with high-risk of developing severe Long COVID can be identified and targeted early. Lastly, the qualitative findings will enhance our understanding toward patient experience and can be used to design more patient- or family-centered care. While the NICE guideline recommends to track Long COVID regularly, it also mentioned that it is still too early to make recommendation of tracing methods based on insufficient evidence. Our quantitative results based on particular instruments and qualitative results based on patient perspectives may provide a reference of selecting appropriate strategies of observing and documenting Long COVID. Table 4 demonstrate the timeline of conducting this research project.

Conclusion

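### The interviews are meant to catch symptoms that the fixed list misses, but interviewees are picked on reports made with that list, so people with only or mainly unlisted symptoms are likely to be missed

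*Combined protocol and SAP*

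**What the plan says.** The Limitations section states the weakness: "As a predetermined list of symptoms will be used to document Long COVID, it is possible that symptoms that" are off the list will be overlooked. It then names the remedy: "The qualitative strand is thus designed and hopefully to close the gap between experienced symptoms and reported symptoms". The Methods list of design characteristics gives a similar reason for adding a qualitative part, namely that quantitative methods alone might miss the phenomenon.

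Interviewees are chosen under Qualitative strand, Recruitment: "Participants who reported considerable symptoms at three-months follow-ups in phase two will be recruited purposively". About 30 are planned. The paragraph gives no score, threshold or instrument for considerable.

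At the regular follow-ups, according to Sampling and Recruitments, "subjects will need to report health status indicators and rate their symptom severity and HRQOL based on selected instruments". The Instruments section names these as the QLQ-C30 and 22 items of the LC29. Anosmia, ageusia and palpitation are checked separately, for existence only. The body of the protocol describes no open symptom item.

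The Abstract puts the invitation rule differently: "Those who did experience COVID-19 symptoms will be invited to join stage three study". That rule is tied neither to the three-month visit nor to a degree of severity.

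**The concern.** A check on a measuring instrument should not be sampled through that instrument. Here the interviews have to reveal what the list leaves out, yet entry to them depends on what was reported at a visit whose described symptom measures are the list. Someone whose main complaint is unlisted may score low, not look considerably symptomatic, and never be asked.

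Two things are at stake. Aim 4 would learn about unlisted symptoms mainly from people who also have marked listed ones. In addition, the cohort has no described place to record an unlisted symptom, so even one found at interview would have no frequency or course across the four time points. The Knowledge Gap section raises a related point about earlier work: "It is possible that some symptoms were ignored if they were not on the lists". The Limitations section does not mention that its own remedy is exposed to the same filter.

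**Working it through.** The question is mainly one of selection logic, so the sections are set side by side first. The only figure in the plan that bears on it, the coverage of the list, is then checked.

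**Selection logic**

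1. Purpose of the interviews (Limitations): find symptoms that the list does not record.
2. Entry to the interviews (Qualitative strand, Recruitment): considerable symptoms reported at the three-month follow-up.
3. What can be reported there (Sampling and Recruitments; Instruments): C30 items, 22 LC29 items, three existence checks and health status indicators.
4. Following 1 to 3 for three kinds of participant:
   - Considerable listed symptoms only: qualifies, but has nothing unlisted to add.
   - Considerable listed symptoms plus unlisted ones: qualifies, and can describe the unlisted ones at interview.
   - Only or mainly unlisted symptoms: low symptom ratings, so unlikely to be picked, and no other route to interview is stated.
5. Under the Abstract's rule the third participant could be invited. The two rules therefore give different answers for exactly the group that matters.

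**Coverage of the list**

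- Stated in Instruments: 29 of 36 self-perceived symptoms, about 81%. Check: 29/36 = 80.6%, which reproduces.
- Not covered by the two questionnaires: 36 − 29 = 7.
- Adding the three existence checks: (29 + 3)/36 = 32/36 = 88.9% recorded in some form.
- Left over: 36 − 32 = 4, and 4/36 = 11.1%, besides any symptom not among the 36.
- Table 1, as it could be read, has 32 rows, of which 28 are marked under at least one instrument. The four unmarked rows are anosmia, ageusia, palpitation and dysphoria. Dysphoria (2% in one of the two source studies) is not among the three checks. Since the text speaks of 36 symptoms, the table as read may be incomplete, and nothing here rests on it.

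These are shares of symptoms, not of people. The documents do not say how many survivors have only or mainly unlisted symptoms, so the size of the group at risk cannot be derived. The Introduction's count of more than 50 does not help, because it mixes signs with symptoms.

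**The case against.** The best defence is that the strand can still do much of its job. Finding unlisted symptoms requires interviewees who have some, not interviewees who have nothing else. The protocol describes Long COVID as multiple and systemic, with fatigue in 22–72% of survivors across studies, so many people with an unlisted symptom may also have a considerable listed one. This stands, and it limits the point to people whose symptoms are only or mainly unlisted.

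A reader might infer more than the documents support, in three ways:

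- *That such people cannot qualify.* The documents do not say so. Considerable is undefined and not expressly tied to instrument scores, sampling is purposive, and the Abstract's rule is broader. Follow-up may be by phone or video, the C30 function and quality-of-life scales could register an unlisted burden, and of the line group the protocol says: "They can communicate with the research team regarding any issues of research or symptoms through line group". None of these is excluded as a route to interview, but none is stated as one either. Discretion that is not written down is not a safeguard.
- *That they are misclassified in aims 2 and 3.* The protocol gives no cut-off for existence of Long COVID, so misclassification is a risk and not an established fact.
- *That the uninterviewed share measures the problem.* Interviews cover 30/118 = 25.4% of the planned cohort. The remaining 74.6% simply reflects the planned numbers and says nothing about how many people have unlisted symptoms.

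It is also fair to say that the list is reasoned: it is mapped to two studies, supplemented by three checks, and its incompleteness is disclosed. Finally, the example questionnaires in appendices A and B are not in the text available here, so one can say only that the body describes no open item.

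**Conclusion.** The point holds in a limited form. The remedy for unlisted symptoms is drawn largely through the list it is meant to check. People with only or mainly unlisted symptoms are likely to be missed, with no stated route to interview, and the Abstract and the Recruitment paragraph disagree on who is invited. The number of people affected is unknown. The protocol's own count leaves 4 of 36 symptoms (11.1%) unrecorded, which suggests a modest gap among known symptoms and says nothing about symptoms outside that count.

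This rests on two assumptions: that considerable symptoms will in practice be judged from the data described for the three-month visit, and that no open item sits in the questionnaires beyond what the body describes. If either is wrong, the gap shrinks and the remaining task is to write the rule down. The point does not undermine the design, but it bears on a purpose the protocol sets for itself and is cheap to repair.

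**What to change.** 1. Add one open item to each follow-up, asking about any other symptom, with the same recall period as the other items and the same 4-point severity rating. A question covering the whole time since COVID-19 would let a resolved symptom count again at later visits and blur the aim 2 course.
2. In the Recruitment paragraph, state how considerable is judged, and let either a listed or an open-item symptom meet it. Align the Abstract with that rule.
3. Report open-item symptoms descriptively under an other category at each time point.
4. Keep the aim 2 and aim 3 outcomes on the planned scales. Open-item symptoms should enter existence or severity at most in a sensitivity analysis, because there is no rule for attributing free text to COVID-19 and adding it would change the scale-based outcome.

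The cost is one extra question per follow-up and the grouping of free-text answers by the existing team. Any follow-up completed before the change would lack the item, and the descriptive report should say so.
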